Study Design

NCT numer: *pending*

Title: Assessment of Vascular Complications in Patients Undergoing Peripheral Revascularization: The Impact of SGLT-2 Inhibitors

Type: Retrospective, observational study

1. **Study Objective:** To assess the impact of SGLT2 inhibitors on vascular complications in patients undergoing peripheral revascularization.

Specific Objective: To evaluate the occurrence of 3-point MACE (Major Adverse Cardiac Events) or MALE (Major Adverse Limb Events) after vascular surgery procedures (both open and minimally invasive), performed electively or urgently, in patients previously treated with SGLT2 inhibitors.

Follow-up period: ONE YEAR: assessment at 30 days, 3 months, and 12 months post-procedure.

Definition of MACE:

Myocardial infarction (MI) not resulting in death

Stroke affecting the central nervous system (CNS) not resulting in death

Cardiovascular death

**Definition of MALE:*

Untreated loss or deterioration of patency in a previously revascularized vessel (decline in ABPI)

Repeat intervention in the revascularized segment due to loss of patency

Amputation (above or below the knee) of the revascularized limb

2. **Primary Outcome Measures:** MALE and MACE

3. **Secondary Outcome Measures:** Individual components of MALE and MACE

4. **Additional Secondary Outcome Measures:**

Surgical complications such as surgical site infection (SSI) or major bleeding

Acute kidney injury

Need for reintervention (readmission and procedure in the same segment)

Foot necrosis

“Minor amputation” (defined as amputation within the foot)

Hospitalization due to heart failure

5. Inclusion and Exclusion Criteria

Inclusion Criteria:

Surgical procedure on peripheral vessels due to acute or chronic ischemia

Use of SGLT2 inhibitors (reason for initiation is irrelevant: CKD – chronic kidney disease / cardiovascular indications / diabetes) - Condition required only for the drug-exposed group.

Ability to follow up the patient for at least 30 days up to 1 year after the vascular procedure

Exclusion Criteria:

Vascular injury as the reason for the procedure

Amputation for reasons other than ischemia (e.g., tumor, neuropathy, trauma without concomitant ischemia)

Planned revascularization procedure not involving lower limbs (e.g., coronary or carotid vessels)

Planned amputation due to ischemia, partial, in the area of the operated limb

Planned other major surgical procedure with high cardiovascular risk

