- d. Deterioration of previously revascularized vessel (ABI decrease) confirmed by visit to vascular surgeon/angiologist
- e. Repeat intervention in previously revascularized segment due to deterioration
- f. Amputation (above or below knee) of revascularized limb
- g. Deep surgical site infection (other than skin)
- h. Major bleeding: at surgical site, gastrointestinal, other (specify location)
- i. Acute kidney injury
- j. Necrosis of the foot
- k. "Minor amputation" (foot or toes)
- l. Hospitalization due to heart failure

8. SGLT2 inhibitor (flozin) continuation during follow-up (up to 1 year):

Did the patient continue taking the flozin as before the procedure?

If not, was it discontinued immediately before surgery or during follow-up? Indicate timing.

9. Hypoglycemia in patients with diabetes:

Were there any hypoglycemic events? (Symptoms confirmed by blood glucose <70 mg/dL or asymptomatic blood glucose <70 mg/dL)

10. Type of procedure performed:

Record the specific vascular intervention.

11. ABI measurements:

Pre-procedure ABI

Post-procedure ABI

ABI if the patient underwent another procedure during follow-up due to restenosis

Notes / Guidelines:

SGLT2 inhibitors (flosins) – include also combination drugs (e.g., Xigduo). If the patient takes a combination drug, mark each component in the Excel sheet (e.g., Lonamo Duo → mark both metformin and DPP-4i; Dipeptidyl Peptidase-4 inhibitors).

If information is unavailable, enter “NZ” to confirm it was checked.

For stroke, include TIA (Transient Ischemic Attack) if confirmed.

*MALE definition, comments: Untreated loss or deterioration of patency in a previously revascularized vessel, measured by: ABI decrease (objective), Restenosis on ultrasound (objective), Shortening of claudication distance (subjective/clinical). Comment: If ABI is not performed at a center, other listed criteria may be used to confirm MALE. ABI is not strictly required if another criterion is met.

**For follow-up events (point 7):

Myocardial infarction not resulting in death, CNS stroke not resulting in death, cardiovascular death, or deterioration of previously revascularized vessel. Comment: “Deterioration requiring

visit and confirmed by physician" is sufficient; ABI measurement is optional but preferred for objective confirmation. Record method of confirmation.

For ABI (point 11): If ABI was not measured at any of the time points, mark "not performed."

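### Item 7d makes a confirming visit part of the deterioration event, but the protocol records no attendance and does not say how an unseen patient is coded, so unequal contact could bias one component of primary MALE

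*Protocol*

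**What the plan says.** The protocol describes a "Retrospective, observational study". Section 1 sets a one-year follow-up with "assessment at 30 days, 3 months, and 12 months post-procedure", without saying that these are vascular visits. Section 2 makes MALE and MACE the primary outcomes.

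Section 1 defines MALE by three components:
- "Untreated loss or deterioration of patency in a previously revascularized vessel (decline in ABPI" (the protocol then closes its bracket)
- "Repeat intervention in the revascularized segment due to loss of patency"
- "Amputation (above or below the knee) of the revascularized limb"

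None of the three mentions a visit. The MALE comment under Notes / Guidelines allows the first to be shown by ABI, ultrasound restenosis or a shorter claudication distance, again with no visit condition.

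The field that collects the first component is section 7, item d: "Deterioration of previously revascularized vessel (ABI decrease) confirmed by visit to vascular surgeon/angiologist". The note to point 7 still ties deterioration to a visit. It accepts confirmation by a physician without naming a specialty, and asks for the method of confirmation.

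The general rule for missing information is to enter NZ. For ABI there is a separate code for a measurement that was not done. Section 11 asks for ABI before and after the procedure, and later only if a further procedure is done for restenosis.

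**The concern.** Untreated deterioration is the MALE component most likely to go unnoticed unless someone examines the patient. Item 7d goes further and makes the visit part of the event. In a retrospective study the protocol cannot cause visits, so whether anyone looked depends on routine care.

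An abstractor who finds no visit has two defensible entries. One is *no*, because the event as worded in 7d did not occur. The other is NZ, because the vessel's state is unknown. The protocol does not choose between them. Recording the method of confirmation helps only for positive events, so a patient seen with a patent vessel and a patient never seen can look the same in the data.

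If unseen patients are entered as *no*, a difference in contact between users and non-users would appear as a difference in deterioration. Section 5 requires SGLT2 inhibitor use, for a renal, cardiovascular or diabetic indication, only in the exposed group. Patterns of care could therefore differ, although the protocol gives no data on this. The gap lies in data collection: if attendance is not abstracted, no later analysis plan can measure it or adjust for it.

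**Working it through.** The protocol gives no sample size, event rate or visit rate, so there is no figure of its own to reproduce. The check has two parts.

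**1. The texts side by side**

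| Place in the protocol | Visit needed for deterioration? | Confirmed by |
|---|---|---|
| Section 1, MALE definition | Not stated | Not stated |
| Notes, MALE comment | Not stated | ABI, ultrasound or claudication distance |
| Section 7, item d | Yes | Vascular surgeon or angiologist |
| Notes, note to point 7 | Yes | Physician, specialty not named |

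The same patient can be an event under one row and not under another. An example is a shorter claudication distance noted by a non-vascular physician.

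**2. Illustration of the size, if unseen patients are entered as *no***

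All inputs are assumptions, equal in both groups except attendance:
- d = 20%, true risk of deterioration alone
- h = 10%, risk of repeat intervention or major amputation, taken as always captured
- v = share of patients seen

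Recorded deterioration = d × v. Recorded MALE = h + d × v. There is no drug effect, so every true ratio is 1.00.

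| Seen, users v non-users | Deterioration | Ratio | MALE | Ratio |
|---|---|---|---|---|
| 90% v 90% | 18% v 18% | 1.00 | 28% v 28% | 1.00 |
| 85% v 80% | 17% v 16% | 1.06 | 27% v 26% | 1.04 |
| 90% v 80% | 18% v 16% | 1.12 | 28% v 26% | 1.08 |
| 90% v 70% | 18% v 14% | 1.29 | 28% v 24% | 1.17 |
| 70% v 90% | 14% v 18% | 0.78 | 24% v 28% | 0.86 |

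For the 90% v 70% row: 0.20 × 0.90 = 0.18 and 0.20 × 0.70 = 0.14, so 0.18 / 0.14 = 1.29. For MALE, (0.10 + 0.18) / (0.10 + 0.14) = 0.28 / 0.24 = 1.17. With an assumed 200 patients per group and a two-sided 5% test, 28% v 24% would be declared different with probability about 0.15 instead of 0.05.

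**If unseen patients are entered as NZ instead**

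Among those seen, the risk is 0.18 / 0.90 = 20% and 0.14 / 0.70 = 20%, ratio 1.00. This holds only if being seen is unrelated to deterioration.

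**The case against.** A reader might infer that the protocol scores every unseen patient as event-free, and that the MALE contrast therefore reflects how often each group was seen. The documents do not support that:
- No text says that a patient without a visit is a *no*. The only rule for absent information is NZ, and a patient nobody examined fits it naturally.
- The vascular-specialist condition is in 7d alone. The note accepts a physician, and the MALE definition has no visit condition.
- Two of the three MALE components do not use 7d.
- Nothing shows that attendance differs by SGLT2 inhibitor use. All patients had a peripheral vascular procedure, and non-users may also have diabetes, renal or cardiac disease. Visits to a diabetologist, cardiologist or nephrologist would not satisfy 7d read strictly.

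The illustration may also run high, because it treats being seen as unrelated to deterioration while worsening patients tend to seek care. If 95% v 90% of deteriorating patients were seen (assumed), the ratios are 0.19 / 0.18 = 1.06 and 0.29 / 0.28 = 1.04.

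Finally, the inclusion criteria ask for follow-up of at least 30 days and up to one year, the protocol closes by stressing that endpoints be assessed, and the handling of NZ in the analysis may be in an SAP that is not shown.

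These points limit the claim but do not remove it. None of them guarantees an examination in each window, says which code applies when there was none, or provides a field for attendance. An SAP can set how NZ is analysed, but it cannot recover who was examined if that was never abstracted.

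**Conclusion.** The concern holds in a limited form. The protocol gives inconsistent conditions for deterioration, leaves the coding of an unseen patient open, and collects nothing that separates examined from unexamined patients. Unequal contact could therefore bias this component and, in diluted form, primary MALE.

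Direction and size are unknown. The ratios apply only if unseen patients are entered as *no* and attendance differs, and both are assumptions. A 20-point attendance gap gives 1.29 for the component and 1.17 for MALE, or 0.78 and 0.86 if reversed. A 5-point gap gives 1.06 and 1.04, and equal attendance gives none. The stronger statement, that the MALE result will measure attendance rather than limb outcome, does not follow from the text. The change is still worth making, because a primary outcome is affected and the information is cheap to collect while the charts are open.

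**What to change.** 1. Reconcile item 7d, the note to point 7, and the MALE definition with its comment, so that one set of conditions decides when deterioration is an event.
2. For each of the 30-day, 3-month and 12-month windows, record from the chart whether a visit or ultrasound that could show deterioration took place.
3. Score 7d as yes, no or not assessed (NZ), and require NZ, never *no*, when there was no such assessment in the window.
4. Report the share assessed in each window by exposure group. NZ alone does not remove bias if patients who deteriorate are more likely to be seen, so readers need this figure.
5. Report MALE limited to repeat intervention or major amputation as a supporting analysis. State that repeat intervention also depends partly on detection, since loss of patency must be found before it is treated.

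The cost is three yes/no fields from charts already being read, one supporting analysis, and some patients whose status on this component becomes unknown.
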